## Proactive Prophylaxis With Azithromycin and Chloroquine in Hospitalised Patients With COVID-19 (ProPAC-COVID)

- With pigment change requires careful dosing and careful control. When using rheumatologic doses, eye examination by an ophthalmologist is recommended before starting treatment and with follow-up to check for any eye manifestations that may arise. Annual monitoring after 5 years of treatment is recommended, however in risk patients initially annual control, see also Chloroquine derivatives (inflammatory rheumatic diseases), side effects.
- With cardiomyopathy can be fatal.
- With macular degeneration is seen and may be irreversible.
- With reversible corneal changes with oedema and blemishes can cause blurred vision or photophobia.
- With blurred vision accommodation is dose-dependent and reversible.
- In malaria treatment and prophylaxis, fewer and milder side effects occur.

\*\*Prolonged QT interval has been seen in patients with particular risk factors for it.

\*\*\*Acute generalized exanthematous pustulosis must be distinguished from psoriasis. Psoriasis exacerbation may occur. May be associated with fever and hyperleukocytosis.

An adverse reaction (AR) is defined as any adverse and undesirable reaction to a trial drug regardless of dose. An adverse event (AE) is defined as any adverse event in a patient or subject in a clinical trial following treatment with a drug, without necessarily linking this treatment to the adverse event.

Since the trial drugs are well known and have been used for many years, we will only record side effects not mentioned in the respective drug summary of the trial drug.

A severe adverse reaction or event (SAR/SAE) is defined as an event or adverse event that, regardless of dose, results in death, is life-threatening, results in hospitalization or prolongs hospitalization, results in significant or persistent disability or incapacity, or leading to a congenital anomaly or malformation.

Investigators must immediately (= within 24 hours) report serious incidents and serious adverse reactions (SAEs and SARs) to the sponsor regardless of whether they are described in the respective product summary. This allows the sponsor to assess the benefits and risks along the way in the study.

Events and adverse events recorded during the period from the patient have received the first dose of trial medication up to and including day 15.

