Recording and reporting of all events and adverse events will end when the trial drug is stopped.

A high degree of comorbidity and death is seen in this patient group and therefore it is also expected that prolonged admissions, re-admissions, NIV, Respirator treatment and death will occur in this patient group. Therefore, these parameters will not be considered as a SAE.

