## Proactive Prophylaxis With Azithromycin and Chloroquine in Hospitalised Patients With COVID-19 (ProPAC-COVID)

All incidents and registered side effects are reported at the end of the trial in a final report to the Danish Medicines Agency. All serious suspected adverse reactions must be reported annually together with a report on the safety of the subjects and sent to the the Danish Medicines Agency (LMST) and the Danish National Committee on Health Research Ethics (VEK).

The product summary of the trial drugs is used to assess whether a serious adverse event is unexpected and thus possibly a Suspected Unexpected Serious Adverse Reactions (SUSAR).

In the event of a fatal or life-threatening SUSAR, this must be registered and reported to LMST and VEK within 7 days of the sponsor becoming aware of it. No later than 8 days after the report, the sponsor must provide LMST and VEK with all relevant information about the sponsors and investigators' follow-up on the event. All other SUSARs are reported to LMST and VEK within 15 days of the sponsor becoming aware of them.

The report must be followed up by a detailed written report, and in both the immediate report and the subsequent report, the investigator must identify the subjects with a personal code number. When reporting deaths, the investigator must provide any additional information that the sponsor may request.

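### Protocol section 6 exempts death, ventilation, prolonged admission and re-admission from SAE status with no exception for suspected drug-related cases, in conflict with its own SAR/SAE definition and SUSAR route

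*Protocol*

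**What the plan says.** All the relevant rules are in protocol section 6 (Side effects, risks and disadvantages).

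- **Seriousness.** One joint definition serves for SARs and SAEs. It covers an event that, among other criteria, "results in death, is life-threatening, results in hospitalization or prolongs hospitalization".
- **24-hour duty.** Investigators must at once "report serious incidents and serious adverse reactions (SAEs and SARs) to the sponsor regardless of whether they are described in the respective product summary".
- **Exemption.** Because comorbidity and mortality are high, "it is also expected that prolonged admissions, re-admissions, NIV, Respirator treatment and death will occur in this patient group". The conclusion follows directly: "Therefore, these parameters will not be considered as a SAE".
- **Entry to SUSAR assessment.** The product summary is "used to assess whether a serious adverse event is unexpected and thus possibly a Suspected Unexpected Serious Adverse Reactions (SUSAR".
- **Expedited route.** "In the event of a fatal or life-threatening SUSAR, this must be registered and reported to LMST and VEK within 7 days" of the sponsor learning of it.
- **Other routes.** "All serious suspected adverse reactions must be reported annually together with a report on the safety of the subjects". Also, "When reporting deaths, the investigator must provide any additional information that the sponsor may request".

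Elsewhere, death counts in the primary endpoint and is a secondary endpoint (protocol 3.3.5; SAP, Primary and Secondary objective and outcomes). An external DSMB sees one interim analysis at about 113 patients with a safety focus (protocol section 4). The SAP's interim paragraph lists selected baseline data, the primary outcome and 30-day all-cause mortality.

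**The concern.** Exempting events that the disease itself often produces is a reasonable way to keep reporting manageable. The difficulty is that this exemption depends on the type of event alone. It asks whether COVID-19 patients commonly have the event, and does so before anyone asks whether the drug might have caused it. Nothing brings a possibly drug-related case back in, and no other case-level route is named.

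This matters because section 6 itself lists torsades de pointes for azithromycin, QT prolongation for both drugs, fulminant hepatitis or liver failure, and a cardiomyopathy that may be fatal. A drug-related death is therefore foreseeable from the protocol's own text. SAE reporting exists to collect cases before causality is settled. If a death need not be reported until someone already suspects the drug, the sponsor may have nothing to assess.

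**Working it through.** The documents state no figure on this point, so the check is a comparison of the rules.

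**1. Definition against exemption.** The joint definition makes death and prolonged hospitalisation serious for both SARs and SAEs. The exemption removes the same outcomes from the SAE category, without a causality condition. The two statements cannot both be applied to a death.

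**2. Two meanings of expected.** The exemption rests on what is expected from the disease in this population. The SUSAR rule rests on what the product summary lists for the drug. A death can be expected in the first sense and unexpected in the second. The text applies the first test and never returns to the second for exempted events.

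**3. Input to the SUSAR rule.** The assessment is worded as starting from a serious adverse event. Death has been taken out of that category. Read literally, where death is the only term, the 7-day fatal-SUSAR rule has no input.

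**4. Two readings of the exemption.** Reading A: it names SAEs only, so SARs are untouched. Reading B: SARs and SAEs share one definition, so an outcome struck out for one is struck out for both. The text does not choose.

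| Case | Reading A | Reading B |
|---|---|---|
| Observed life-threatening arrhythmia or liver failure, then death | Reportable: the underlying event is not on the exempted list | Reportable, same reason |
| Death that the investigator already suspects is drug-related | Reportable within 24 hours as a SAR; entry to SUSAR assessment unclear | Not clearly reportable |
| Unwitnessed sudden death, no other term, no view yet on cause | Reportable only if someone raises suspicion; no rule requires the question | Not reportable |

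The third row is the gap under either reading, and the second shows where sites could differ.

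**5. What would be lost.** If the product summary lists the underlying reaction, it is not a SUSAR in any case. The loss is then the 24-hour report and possibly the annual one. If the cause is unlisted, the 7-day report is also at risk.

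**6. Recording window.** Section 6 says in one place that events are recorded through day 15, and in another that recording ends once trial drug is stopped. Protocol 3.3.4 provides for stopping trial drug on a QTc finding while the patient stays in the study. A death between such a stop and day 15 is inside the window by one sentence and outside it by the other.

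**7. Scale only.** N = 226, 113 per arm (protocol 3.3.6). All-cause deaths = N × mortality.

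- At 25%, the protocol's background estimate for admitted patients in China (section 2.1): 226 × 0.25 = 56.5, or 113 × 0.25 = 28.25 per arm.
- At an assumed 10%: 226 × 0.10 = 22.6.
- At an assumed 5%: 226 × 0.05 = 11.3.

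These are deaths from any cause. The 25% is not a day-15 rate, and the trial excludes patients on more than 5 L of oxygen per minute. None of these figures estimates drug-suspected deaths, for which the documents give no basis.

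**The case against.** The best defence is that the exemption concerns SAEs only. It does not mention SARs or SUSARs. SARs have their own place in the 24-hour duty, fatal SUSARs keep their 7-day rule, all serious suspected reactions go into the annual report, and a sentence on reporting deaths shows that such reports were foreseen. The reason given for the exemption is disease background, so the authors may well have meant only disease-related events. Deaths are also not unwatched: they enter the endpoints, and the DSMB sees 30-day mortality by group. QTc is reviewed on treatment, and the SAP reports QTc above 500 ms and ventricular arrhythmias by arm.

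Much of this stands. A reader might infer that a drug-caused death could never reach the 24-hour report, that the fatal-SUSAR rule cannot operate at all, or that every death in the window escapes causality review. The documents do not support those readings, because the routes just named remain on the page. Nor do they support saying that a fatal arrhythmia would count only as an efficacy outcome: a life-threatening arrhythmia is not on the exempted list and is serious in its own right.

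What the defence does not supply is a rule that makes anyone ask about causality when death is the only term. The SAR route works only once suspicion exists. The mortality comparison is an aggregate at one time point, and the SAP's interim list names neither SAE review nor causality assessment. The arrhythmia counts are not on that list either.

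**Conclusion.** The concern holds as an internal conflict in a stated rule. Section 6 exempts five outcomes from SAE status with no exception for suspected drug-related cases. This contradicts its SAR/SAE definition and removes death from the category in which SUSAR assessment begins. A suspected drug-related death may therefore go unreported within 24 hours and unassessed, and practice may vary between sites.

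It is a risk of missed cases, not a certainty. How many would be affected cannot be derived from the documents, and the conclusion does not depend on the number. It rests on a site applying the exemption as written, and on there being no separate safety instruction, outside the protocol and SAP, that restores the causality question. Because it concerns participant safety and is cheap to correct, it should be corrected.

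**What to change.** Reconcile the definition, exemption and SUSAR paragraphs of protocol section 6 by stating that:

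- the exemption covers only events that the blinded investigator judges to be due to COVID-19 or underlying disease;
- any death, NIV, respirator treatment, prolonged admission or re-admission with a reasonable possibility of relation to study drug stays within SAE, SAR and SUSAR reporting, including the 24-hour report;
- a causality assessment is recorded for each exempted event.

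The two statements on when event recording ends should be reconciled in the same edit. Add counts of exempted events by arm to the DSMB interim report, which already includes 30-day mortality.

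The cost for the exemption itself is one protocol sentence, one CRF field and slightly more reporting work for sites and sponsor. Sample size, endpoints and the analysis of efficacy do not change.

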## Proactive Prophylaxis With Azithromycin and Chloroquine in Hospitalised Patients With COVID-19 (ProPAC-COVID)

All incidents and registered side effects are reported at the end of the trial in a final report to the Danish Medicines Agency. All serious suspected adverse reactions must be reported annually together with a report on the safety of the subjects and sent to the the Danish Medicines Agency (LMST) and the Danish National Committee on Health Research Ethics (VEK).

The product summary of the trial drugs is used to assess whether a serious adverse event is unexpected and thus possibly a Suspected Unexpected Serious Adverse Reactions (SUSAR).

In the event of a fatal or life-threatening SUSAR, this must be registered and reported to LMST and VEK within 7 days of the sponsor becoming aware of it. No later than 8 days after the report, the sponsor must provide LMST and VEK with all relevant information about the sponsors and investigators' follow-up on the event. All other SUSARs are reported to LMST and VEK within 15 days of the sponsor becoming aware of them.

The report must be followed up by a detailed written report, and in both the immediate report and the subsequent report, the investigator must identify the subjects with a personal code number. When reporting deaths, the investigator must provide any additional information that the sponsor may request.

### **7. Economy:**

The research project is (investigator) initiated by COP:TRIN. Funding has been obtained from the Novo Nordisk Foundation of DKK 2.2 million for sponsor, remuneration of auxiliary personnel, payment of laboratory tests and equipment, as well as for manufacture of IMP treatment and placebo. The sponsors and investigators are not financially linked to private companies, foundations, etc. in this research project.

Medical expenses are covered, if not obtained from other sources, by the section for respiratory medicine research, Gentofte Hospital.

To the extent possible, the section for respiratory medicine research, Gentofte Hospital supports follow-up for endpoints and otherwise by appointment.

### **8. Remuneration:**

Patients are not paid for participation in the trial.

### **9. Availability of information and right to data:**

The consent gives the primary investigator, monitor and any control authority direct access to obtain information in the patient's medical record, etc., including electronic record, in order to see

## Proactive Prophylaxis With Azithromycin and Chloroquine in Hospitalised Patients With COVID-19 (ProPAC-COVID)

information about the subject's health conditions which are necessary as part of the implementation of the research project and for control purposes, including self-monitoring, quality-control etc.

The project group that has designed and conducted this study has the right to data and the right (and duty) to publish based on data. Project management manages data and invites members of the study group to publications. All sites that recruit patients are entitled to at least one authorship on the primary publication, and for every 10 patients recruited, the site is entitled to an extra authorship. Sites that have not participated in the design of the study are entitled to a maximum of 3 authorships. It is the opinion of the steering committee that knowledge sharing creates more and better scientific results. Requests for knowledge sharing from other groups may be submitted to Project Management ([name], [name], [name]) who will evaluate primarily and who, if the project is found suitable, will discuss it with the COP:TRIN Steering Committee.

Project Management has the first right to undertake sub-studies but may well assign projects to other contributors. In that case, the following considerations will be significant in the assessment: 1) Participation in the design phase of this RCT and at what level, and 2) Number of patients recruited at a site. If the hypothesis to be investigated is not planned to be examined by our group, we will allow the use of our data if the Steering Committee finds the project scientifically sound and, if appropriate, a collaboration with members of the COP:TRIN Steering Committee will be proposed. However, it should be emphasized that data is used for a specific purpose, not for future purposes in general. This becomes conditional by the steering committee for data to be used in a sound way to test hypotheses with relevant scientific content.

Information regarding subjects are processed and stored in accordance with the **Data Protection Regulation (GDPR)**, the Data Protection Act and the Health Act and the project is properly notified in accordance with applicable rules and laws to the appropriate authorities.

### **10. Publication of results:**

All project results will be sought published in scientific contexts, including international journals. This will happen regardless of whether the result is positive, negative or inconclusive.

### **11. Scientific Ethics Statement:**

The study is conducted in accordance with the Declaration of Helsinki and is carried out in accordance with the rules of the Personal Data Act and the Health Act. The study has been registered at the Danish Data Protection Agency.

## Proactive Prophylaxis With Azithromycin and Chloroquine in Hospitalised Patients With COVID-19 (ProPAC-COVID)

Recruitment and inclusion will take place as previously described (section 3.3.1). Participation requires a signed statement of consent. Patients can withdraw their participation consent and withdraw from the research project at any time without this having any effect on their right to current or future treatment. Furthermore, the patient is entitled to bring a bystander to the information interview and is entitled to reflection time before any declaration of consent is signed.

The important objective of the study is to investigate whether pro-active and *pre-emptive* treatment against COVID-19 can reduce the length of hospitalisation and the risk of intensive care and improve the survival of patients - an area that has so far been poorly researched and where the need for evidence-based guideline for handling and processing is large and very urgent.

Potential disadvantages and side effects are described in the separate section 5. Among other things, it appears that the likelihood of serious adverse reactions to both treatment and examinations is rare. In addition, the treating physician can always discontinue treatment if it is considered contraindicated.

Placebo is given patients allocated to the control group as no specific standard medical treatment is available.

The experimental method and statistical analyses have been carefully considered in order to be able to disseminate and apply relevant and secure research results to clinical practice.

Based on the above considerations, we believe that the experiment is ~~sound~~ ethically sound and can be conducted without exposing the test participant to unjustifiable risks.

### **12. Recruitment of subjects and informed consent**

At each trial centre, screening of patients admitted with a positive SARS-CoV-2 test is performed. Patients are assessed against the inclusion and exclusion criteria of the attending physician who receives the patient's consent to contact the investigator. The Investigator then contacts the patient for recruitment to the study. Disclosure of information about the study and obtaining informed consent may also be undertaken by other healthcare professionals. This includes research assistants (medical students), clinical nursing specialists and project nurses (See below for specific requirements). These are all separately trained in the task and have the opportunity to call a physician should any medical issues arise. They can also contact the coordinating investigator as well as a hotline team for the trial should any questions arise about informed consent. This hotline is available 24 hours a day. All patients are offered a consultation with a physician if they ask for it. For project nurses, the following applies specifically: i) must have at least 5 years of seniority. These requirements are verified by primary investigator from each site that afterwards creates a document for these individuals from which the above specific requirements are verified. This document is dated and signed.

## Proactive Prophylaxis With Azithromycin and Chloroquine in Hospitalised Patients With COVID-19 (ProPAC-COVID)

If a patient is considered suitable, the person will be invited to participate in the project. Participation in the trial is voluntary. Informed consent is obtained from the participants of the trial acc. to Executive Order No. 1149 of 30 September 2013 on information and consent for participation in health science research projects and on notification and supervision of health science research projects. The first contact with the the potential participant in the trial will be at admission to one of the participating departments. Participant information is provided both orally and in writing, and the patient is informed that they are entitled to 24 hours of reflection time before consent is given for participation in the trial. Participants who wish to do so themselves after the period of reflection time may give consent in connection with the information meeting.

The right to a bystander is ensured by the patient being able to bring a bystander, however, subject to COVID isolation rules. If no bystanders come to the first call, they are ensured afterwards to a bystander, when the patient is out of isolation. It is ensured that the conversations are undisturbed by using the patient's isolation room. If the doctor carries a "pager" or telephone, these are handed in prior to the call. The trial participant will be provided with the document "The research subject's rights in a health science research project", which contains information about confidentiality, access to documents and access to complaints. The subjects are protected under the Personal Data Processing Act. The trial has been reported to the Regional Science Ethics Committee, the Danish Medicines Agency and the Danish Data Protection Agency.

It must be ensured at all times that subjects have consented to participate in clinical trials. If an isolated subject with COVID-19 can sign consent declaration via electronic tool, this can be used instead of consent with signature. This can be, for example, a mobile phone, an iPad, a laptop with secure identification, for example by an easy ID (or other solution that meets the OCES standard). If the above described solution is not possible, the following solutions can be used as temporary documentation for the consent:

- Copy of signed consent declaration – e.g. using camera: The subject can sign the consent form as usual. Since the signed form must not leave the isolation room, the signature can be documented in the form of a photograph of the signed form, for example through a window.
- If the test subject cannot sign the consent declaration himself, e.g. due to problems with having electronic equipment in the room, or obtaining documentation for the consent out of the room, the witness can sign on behalf of the subject: If the subject verbally consents, a witness can on behalf of the subject sign the consent form. For both of the above solutions, documentation (photo and witness signature) will be filed in the investigator's section of the Trial Master File (TMF). Furthermore, it is ensured that the Data Protection Regulation and the Data Protection Act are complied with, although documentation of the consent is temporarily different than it usually is. If the situation is normalised, the correct signed consent form must be obtained from the subject as soon as possible.

